11.2 Safety Reporting Requirements

██████████ is responsible for ensuring that safety events (adverse events, product complaints and other safety findings) reported by the HCP or interviewer that occur in patients treated with Blincyto after study enrollment through the final study contact and

Approved

submitted as individual case safety reports to Amgen via the applicable Amgen Safety Reporting Form (paper form) within 1 business day of awareness.

See [Appendix C](#) for sample Safety Report Form(s), [Appendix D](#) for Additional Safety Reporting Information regarding the adverse event grading scale used in this study, and [Appendix E](#) for sample Pregnancy and Lactation Notification Worksheets.

The HCP may be asked to provide additional information for any event submitted, which may include a discharge summary or extracts from the medical record. Information provided about the event must be consistent with the medical records.

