9.2.1 Study Period

The maximum planned period for data collection is 23 months. However, as product launch is planned in a staggered manner in Europe, this period is expected to be reduced in some countries.

As this is a one-wave cross-sectional design, data from HCPs will be collected at one point in time.

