9.2.3.1 Inclusion Criteria

- Physician, nurse or pharmacist has managed, administered or prepared Blincyto for at least one adult patient with Ph- R/R B precursor ALL.

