9.2.4 Baseline Period

This study consists of three cross-sectional surveys that do not involve any follow-up. Eligibility criteria will be assessed and HCP questionnaires will be completed at one point in time within the data collection period.

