9.3 Variables

The surveys will examine the effectiveness of the educational materials targeting physicians, nurses and pharmacists about the risks associated with Blincyto treatment and the best course of action to undertake in order to minimise these risks.

Three questionnaires will contain multiple-choice questions with no free text fields.

Approved

The questionnaire will be structured as follows:

- A. Acceptance to participate (date and signature)
- B. Screening: eligibility, demographics
- C. Main questionnaire domains

Section B (Screening) will collect socio-demographic characteristics (age group, gender and experience) about HCPs to explore factors associated with understanding and implementation of key messages. The questionnaire will be designed to take a maximum of 15 minutes to complete.

The questionnaire will assess the following key concepts related to each of the brochures:

- Receipt of the brochures.
- Knowledge and understanding of key messages.
- Behaviors outlined in the brochures including the distribution of educational brochures to patients/caregivers.
- Usage of the brochures ie, whether HCPs read and refer to the educational materials and reasons for not reading them.

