9.7.2.3.1 Description of Study Enrollment

The study populations as identified in the recruitment process for each of the HCP surveys will be described. Recruitment rates and a description of the number of subjects in the study and analysis populations will be provided.

Analysis sets: As shown in [Figure 2](#), datasets for analysis will be further described in the SAP and will include:

- Study population: Physicians, nurses and pharmacists identified and potentially willing/eligible to participate.
- Eligible Set: All physicians, nurses and pharmacists who fulfill the eligibility criteria.
- Enrolled Set: All eligible physicians, nurses and pharmacists who agree to participate in the study and access the electronic survey.
- Full Analysis Set: All physicians, nurses and pharmacists who complete the questionnaire of their corresponding survey and have valid responses to allow for the assessment of the primary objective.

Figure 2. Study Population and Datasets Flow-chart

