11.1.3 Other Safety Findings

Other Safety Findings (regardless of association with an adverse) include:

- Medication errors, overdose, whether accidental or intentional, misuse, or abuse, , involving an Amgen product,
- Pregnancy and lactation exposure,
- Transmission of infectious agents,
- Reports of uses outside the terms for authorized use of the product including off-label use,
- Occupational exposure,
- Any lack or loss of intended effect of the product(s).

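### Section 11.2 ties the safety-reporting duty to events that occur after enrollment, which does not fit a one-wave survey of professionals about past Blincyto use

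*Protocol*

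**What the plan says.** Section 11.2 covers adverse events, product complaints and other safety findings reported by the healthcare professional (HCP) or an interviewer, "that occur in patients treated with Blincyto after study enrollment through the final study contact". They are to reach the sponsor "within 1 business day of awareness". In the text at hand the sentence has no verb for the safety events before it turns to their submission.

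Section 11.1.3 places these among the other safety findings: "Medication errors, overdose, whether accidental or intentional, misuse, or abuse".

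The design sections describe a study with a single data collection and no observation time:

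- Section 9.2.1: "As this is a one-wave cross-sectional design, data from HCPs will be collected at one point in time".
- Section 9.2.4: "This study consists of three cross-sectional surveys that do not involve any follow-up".
- Section 9.2.3.1, the only inclusion criterion: "Physician, nurse or pharmacist has managed, administered or prepared Blincyto for at least one adult patient with Ph- R/R B precursor ALL".
- Section 9.1 starts distribution 12 to 18 months after launch in each country.
- Section 9.9 accepts recall bias because the questions concern the past.

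The introduction to Section 11 expects very few reports of adverse events and medication errors, but not none.

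**The concern.** A window from enrollment to last contact belongs in a study that enrolls patients and observes them forward. Here HCPs are enrolled, nobody is followed, and respondents qualify through what they have already done. If one of them mentions a pump error or a neurological event, it will usually have happened before that person joined the survey. A rule that turns on when the event occurred then leaves it out.

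Medication errors are one of the two risks for which the brochures were required (Section 7.1). A post-authorisation safety study of those brochures should not carry a reporting rule that, on its wording, omits most medication errors disclosed through it. At stake is what the coordinating centre is obliged to forward. No endpoint, precision figure or analysis depends on it.

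**Working it through.** The plan gives no figure to reproduce here. The check sets Section 11.2 beside the design sections and tries each reading that the incomplete sentence allows.

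**Inputs**

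- Start of the survey: 12 to 18 months after country launch (Section 9.1).
- Data collection: at most 23 months, expected to be shorter in some countries (Section 9.2.1).
- Contacts: one data collection per HCP, no follow-up (Sections 9.2.1 and 9.2.4).
- Eligibility: past use of Blincyto (Section 9.2.3.1).
- Interviewers: only in the linguistic validation (Section 9.3.3).
- Exclusion: anyone who took part in pre-testing (Section 9.2.3.2). I take the validation interviews to be part of pre-testing.

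**Reading 1: the event must occur between the HCP's own enrollment and last contact.** This is the plainest sense, since the verb is to occur. The use that made the HCP eligible lies before the window. Only an event that happens while that person is taking part would count.

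**Reading 2: the window is the whole data collection period.** This is the most generous reading of an occurrence window. Let L be the months from launch to the start of collection, and t the months into collection when the HCP answers. The share of calendar time since launch that lies outside the window is L / (L + t).

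| HCP answers at | L = 12 | L = 18 |
|---|---|---|
| Start, t = 0 | 12/12 = 100% | 18/18 = 100% |
| Midpoint, t = 11.5 | 12/23.5 = 51% | 18/29.5 = 61% |
| Last day, t = 23 | 12/35 = 34% | 18/41 = 44% |

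Where collection is shorter than 23 months, the last-day share is larger. These are shares of time, not of events, because the documents do not say how use is spread after launch.

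**Reading 3: the time phrase belongs to the treatment of the patients.** Patients whose treatment ended before enrollment are then outside the duty.

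**Reading 4: the time phrase limits when the report is received.** Earlier events would then be covered, and the clock that runs from awareness fits this sense. But the sentence attaches the time phrase to occurrence. A gap also remains for the interviewer, whom the rule names as a source. The participants of the validation interviews are barred from the survey, so they never enroll and have no window.

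**Other text.** No section shown extends collection to events before enrollment. Section 11.2.1 governs the sponsor's onward reporting to authorities. It does not define what the coordinating centre must collect and forward.

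Each of the four readings leaves out something that the rule appears meant to catch.

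**The case against.** The strongest reply is that the sentence cannot be held to a literal meaning, because words are missing. In the text at hand a page break falls close to the gap, so a word may even have been lost in conversion. With the verb restored, the time phrase might limit the receipt of reports, as in Reading 4. That ambiguity is real, and it is part of the reason to rewrite the sentence. It does not remove the problem, because the words that are present speak of events that occur, and Reading 4 still leaves out the interviewer.

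A second reply is that other text makes loss of a report unlikely. The definitions in Sections 11.1.1 to 11.1.4 carry no enrollment limit. The sample form in Appendix C, marked for vendor surveys of health care professionals, has open date fields. The brochures ask HCPs to report suspected adverse reactions. Section 11.2.1 commits the sponsor to pharmacovigilance guidelines. This stands as mitigation. It does not repair the coordinating centre's own duty.

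A third reply is that the volume is very small. The questionnaires are multiple choice without free text (Section 9.3), and few reports are expected. This also stands.

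Three stronger claims are tempting, and the documents do not support them:

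- **The window is 15 minutes.** A reader might join the Enrolled Set, "All eligible physicians, nurses and pharmacists who agree to participate in the study and access the electronic survey", to the length limit, "The questionnaire will be designed to take a maximum of 15 minutes to complete". But the first is an analysis-set definition, and Section 11.2 does not define enrollment. Nothing says that submission is the final contact. Section 11.2 foresees later requests for information, and Section 9.4 lets respondents pause without a stated limit.
- **Recruiters telephone HCPs about past handling.** Section 9.2.2 uses the telephone only to reach non-responders after two mailings.
- **The 6/189 (3.2%) medication errors in the pivotal trial indicate how many reports are at risk.** That is a frequency per trial patient. It says nothing about how often HCPs would disclose events in this survey.

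**Conclusion.** The point holds as a defect of wording with a practical consequence. Section 11.2 is incomplete. As worded, it limits the coordinating centre's duty to a period that does not fit Sections 9.2.1, 9.2.3.1 and 9.2.4. Most adverse events and medication errors that a respondent could disclose would fall outside it. On the most generous occurrence window, at least 34% to 44% of the time since launch is still excluded for an HCP who answers on the last day, and more for anyone who answers earlier.

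This rests on taking the verb in the sentence at its word and on counting the validation interviews as pre-testing. A reader might infer that disclosed events would be discarded or would never reach the authorities. The documents do not show that. They show only that the stated duty does not cover those events. The expected number of reports is very low, and no endpoint estimate changes.

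**What to change.** Complete the sentence in Section 11.2 and reconcile it with Sections 9.2.1, 9.2.3.1 and 9.2.4 by keying the duty to awareness instead of to the date of the event. Suggested wording:

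*The coordinating centre will submit to the sponsor, within 1 business day of awareness, any adverse event, product complaint or other safety finding involving Blincyto of which it or an interviewer becomes aware during the conduct of the study, including the linguistic validation interviews, whenever the event occurred.*

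This keeps the existing time limit and the existing form, gives the mention of an interviewer a purpose, and makes definitions of enrollment and final contact unnecessary for this rule. Naming the validation interviews states a scope that the present text leaves unclear, so the sponsor should confirm that it is intended. The cost is one sentence and possibly a few more reports to process.

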11.2.1 Safety Reporting Requirement to Regulatory Bodies

Amgen will report safety data as required to regulatory authorities, Investigators/institutions, IRBs/IECs or other relevant ethical review board(s) in accordance with Pharmacovigilance guidelines and in compliance with local regulations. The Investigator is to notify the appropriate IRB/IEC or other relevant ethical review board of Serious Adverse Events in accordance with local procedures and statutes.

12. Administrative and Legal Obligations

12.1 Protocol Amendments and Study Termination

Amgen may amend the protocol at any time. If Amgen amends the protocol, written agreement from the Investigator must be obtained where applicable per local governing law and/or regulations.

Amgen reserves the right to terminate the study at any time. Both Amgen and the Investigator reserve the right to terminate the Investigator's participation in the study according to the contractual agreement.

13. Plans for Disseminating and Communicating Study Results

The protocol, study status updates and report(s) will be included in regulatory communications according to the risk minimisation plan, periodic benefit-risk evaluation reports and other regulatory milestones and requirements.

This study will be registered on the European Network of Centres for Pharmacoepidemiology and Pharmacovigilance (ENCePP) website before the start of data collection, and the study summary results will be posted on this public website no later than 12 months after study termination (defined as 'database lock').

Approved

A final study report will be developed and submitted to PRAC, and will serve as a basis for the development of publications and presentations in scientific journals, and press releases.

Abstracts, summaries, presentations and manuscripts will be prepared in line with dissemination guidelines of the International Committee of Medical Journal Editors (International Committee of Medical Journal Editors) and Guidelines for Good Pharmacoepidemiology Practice ([International Society for Pharmacoepidemiology 2008](#)) to help ensure the quality and integrity of pharmacoepidemiological research and to provide adequate documentation of research methods and results.

13.1 Publication Policy

The results of this study will be submitted for publication. Authorship of any publications resulting from this study will be determined on the basis of the International Committee of Medical Journal Editors (ICJME) Recommendations for the Conduct, Reporting, Editing and Publication of Scholarly Work in Medical Journals, which states:

- Authorship credit should be based on (1) substantial contributions to conception and design, acquisition of data, or analysis and interpretation of data; (2) drafting the article or revising it critically for important intellectual content; (3) final approval of the version to be published and (4) agreement to be accountable for all aspects of the work in ensuring that questions related to the accuracy or integrity of any part of the work are appropriately investigated and resolved. Authors should meet conditions 1, 2, and 3 and 4.
- When a large, multicenter group has conducted the work, the group should identify the individuals who accept direct responsibility for the manuscript. These individuals should fully meet the criteria for authorship defined above.
- Acquisition of funding, collection of data, or general supervision of the research group, alone, does not justify authorship.
- All persons designated as authors should qualify for authorship, and all those who qualify should be listed.
- Each author should have participated sufficiently in the work to take public responsibility for appropriate portions of the content.

All publications (eg, manuscripts, abstracts, oral/slide presentations, book chapters) based on this study must be submitted to Amgen for corporate review. The vendor agreement will detail the procedures for, and timing of, Amgen's review of publications.

14. Compensation

Healthcare professionals will receive incentives for their participation in the surveys. This compensation will be based on a Fair Market Value (FMV) assessment (eg, time and effort) in each participating country.

Approved

15. References

Benjamin, J.E. & Stein, A.S., 2016. The role of blinatumomab in patients with relapsed/refractory acute lymphoblastic leukemia. *Therapeutic Advances in Hematology*, 7(3), pp.142–156.

CIOMS, 2014. *Practical approaches to risk minimisation for medicinal products: Report of CIOMS Working Group IX*, Geneva, Switzerland.

Appendix A. List of Stand-alone Documents

No.	Title
1	Physician questionnaire
2	Nurse questionnaire
3	Pharmacist questionnaire

Approved

Appendix B. ENCePP Checklist for Study Protocols

EUROPEAN MEDICINES AGENCY
 SCIENCE MEDICINES HEALTH

European Network of Centres for
 Pharmacoepidemiology and
 Pharmacovigilance

Doc.Ref. EMA/540136/2009

ENCePP Checklist for Study Protocols (Revision 3)

Adopted by the ENCePP Steering Group on 01/07/2016

The [European Network of Centres for Pharmacoepidemiology and Pharmacovigilance \(ENCePP\)](#) welcomes innovative designs and new methods of research. This Checklist has been developed by ENCePP to stimulate consideration of important principles when designing and writing a pharmacoepidemiological or pharmacovigilance study protocol. The Checklist is intended to promote the quality of such studies, not their uniformity. The user is also referred to the [ENCePP Guide on Methodological Standards in Pharmacoepidemiology](#), which reviews and gives direct electronic access to guidance for research in pharmacoepidemiology and pharmacovigilance.

For each question of the Checklist, the investigator should indicate whether or not it has been addressed in the study protocol. If the answer is "Yes", the section number of the protocol where this issue has been discussed should be specified. It is possible that some questions do not apply to a particular study (for example, in the case of an innovative study design). In this case, the answer 'N/A' (Not Applicable) can be checked and the "Comments" field included for each section should be used to explain why. The "Comments" field can also be used to elaborate on a "No" answer.

This Checklist should be included as an Annex by marketing authorisation holders when submitting the protocol of a non-interventional post-authorisation safety study (PASS) to a regulatory authority (see the [Guidance on the format and content of the protocol of non-interventional post-authorisation safety studies](#)). The Checklist is a supporting document and does not replace the format of the protocol for PASS as recommended in the Guidance and Module VIII of the Good pharmacovigilance practices (GVP).

Study title: Survey of physicians, pharmacists, and nurses involved in the prescribing, preparation and administration of Blincyto in Europe to evaluate the effectiveness of additional risk minimization measures

Study reference number:

Section 1: Milestones	Yes	No	N/A	Section Number
1.1 Does the protocol specify timelines for				
1.1.1 Start of data collection ¹				6
1.1.2 End of data collection ²				6
1.1.3 Study progress report(s)				
1.1.4 Interim progress report(s)				
1.1.5 Registration in the EU PAS register				6
1.1.6 Final report of study results.				6

¹ Date from which information on the first study is first recorded in the study dataset or, in the case of secondary use of data, the date from which data extraction starts.

² Date from which the analytical dataset is completely available.

ENCePP Checklist for Study Protocols (Revision 3)

Approved

Comments:

This is a cross-sectional study and thus neither study progress reports nor interim progress reports are expected to be developed during the study conduct.

Section 2: Research question	Yes	No	N/A	Section Number
2.1 Does the formulation of the research question and objectives clearly explain:				
2.1.1 Why the study is conducted? (e.g. to address an important public health concern, a risk identified in the risk management plan, an emerging safety issue)				4, 7
2.1.2 The objective(s) of the study?				4, 8
2.1.3 The target population? (i.e. population or subgroup to whom the study results are intended to be generalised)				4, 9.2
2.1.4 Which hypothesis(-es) is (are) to be tested?				
2.1.5 If applicable, that there is no a priori hypothesis?				

Comments:

This study is descriptive and therefore no formal hypothesis will be tested.

Section 3: Study design	Yes	No	N/A	Section Number
3.1 Is the study design described? (e.g. cohort, case-control, cross-sectional, new or alternative design)				4, 9.1
3.2 Does the protocol specify whether the study is based on primary, secondary or combined data collection?				4, 9.1
3.3 Does the protocol specify measures of occurrence? (e.g. incidence rate, absolute risk)				
3.4 Does the protocol specify measure(s) of association? (e.g. relative risk, odds ratio, excess risk, incidence rate ratio, hazard ratio, number needed to harm (NNH) per year)				
3.5 Does the protocol describe the approach for the collection and reporting of adverse events/adverse reactions? (e.g. adverse events that will not be collected in case of primary data collection)				11

Comments:

Section 4: Source and study populations	Yes	No	N/A	Section Number
4.1 Is the source population described?				9.2
4.2 Is the planned study population defined in terms of:				
4.2.1 Study time period?				4, 9.2.1
4.2.2 Age and sex?				4, 9.2.3
4.2.3 Country of origin?				4, 9.1, 9.2

ENCePP Checklist for Study Protocols (Revision 3)

Approved

Section 4: Source and study populations	Yes	No	N/A	Section Number
4.2.4 Disease/indication?				4, 9.2.3
4.2.5 Duration of follow-up?				
4.3 Does the protocol define how the study population will be sampled from the source population? (e.g. events or inclusion/exclusion criteria)				4, 9.2.2

Comments:

This is a cross-sectional design with no follow-up.

Section 5: Exposure definition and measurement	Yes	No	N/A	Section Number
5.1 Does the protocol describe how the study exposure is defined and measured? (e.g. operational details for defining and categorising exposure, measurement of dose and duration of drug exposure)				
5.2 Does the protocol address the validity of the exposure measurement? (e.g. precision, accuracy, use of validation sub-study)				
5.3 Is exposure classified according to time windows? (e.g. current user, former user, non-use)				
5.4 Is exposure classified based on biological mechanism of action and taking into account the pharmacokinetics and pharmacodynamics of the drug?				

Comments:

No exposure-outcome association will be assessed

Section 6: Outcome definition and measurement	Yes	No	N/A	Section Number
6.1 Does the protocol specify the primary and secondary (if applicable) outcome(s) to be investigated?				4, 9.3
6.2 Does the protocol describe how the outcomes are defined and measured?				4, 9.3
6.3 Does the protocol address the validity of outcome measurement? (e.g. precision, accuracy, sensitivity, specificity, positive predictive value, prospective or retrospective ascertainment, use of validation sub-study)				4, 9.3
6.4 Does the protocol describe specific endpoints relevant for Health Technology Assessment? (e.g. HRQoL, QALYs, DALYs, health care services utilisation, burden of disease, disease management)				

Comments:

This is a cross-sectional survey with no HEOR objectives

Section 7: Bias	Yes	No	N/A	Section Number
7.1 Does the protocol describe how confounding will be addressed in the study?				

ENCePP Checklist for Study Protocols (Revision 3)

Approved

Section 7: Bias	Yes	No	N/A	Section Number
7.1.1. Does the protocol address confounding by indication if applicable?				
7.2 Does the protocol address:				9.9
7.2.1. Selection biases (e.g. healthy user bias)				9.9
7.2.2. Information biases (e.g. misclassification of exposure and endpoints, time-related bias)				9.9
7.3 Does the protocol address the validity of the study covariates?				

Comments:

No strenght of association between exposure and outcome is measured

Section 8: Effect modification	Yes	No	N/A	Section Number
8.1 Does the protocol address effect modifiers? (e.g. collection of data on known effect modifiers, sub-group analyses, anticipated direction of effect)				9.7

Comments:

Section 9: Data sources	Yes	No	N/A	Section Number
9.1 Does the protocol describe the data source(s) used in the study for the ascertainment of:				
9.1.1 Exposure? (e.g. pharmacy dispensing, general practice prescribing, claims data, self-report, face-to-face interview)				9.4
9.1.2 Outcomes? (e.g. clinical records, laboratory markers or values, claims data, self-report, patient interview including scales and questionnaires, vital statistics)				9.4
9.1.3 Covariates?				9.4
9.2 Does the protocol describe the information available from the data source(s) on:				
9.2.1 Exposure? (e.g. date of dispensing, drug quantity, dose, number of days of supply prescription, daily dosage, prescriber)				9.4
9.2.2 Outcomes? (e.g. date of occurrence, multiple event, severity measures related to event)				9.4
9.2.3 Covariates? (e.g. age, sex, clinical and drug use history, co-morbidity, co-medications, lifestyle)				9.4
9.3 Is a coding system described for:				
9.3.1 Exposure? (e.g. WHO Drug Dictionary, Anatomical Therapeutic Chemical (ATC) Classification System)				
9.3.2 Outcomes? (e.g. International Classification of Diseases (ICD)-10, Medical Dictionary for Regulatory Activities (MedDRA))				
9.3.3 Covariates?				
9.4 Is a linkage method between data sources described? (e.g. based on a unique identifier or other)				9.6.2

ENCePP Checklist for Study Protocols (Revision 3)

Approved

Comments:

--

Section 10: Analysis plan	Yes	No	N/A	Section Number
10.1 Is the choice of statistical techniques described?				4, 9.7
10.2 Are descriptive analyses included?				4, 9.7
10.3 Are stratified analyses included?				4, 9.7
10.4 Does the plan describe methods for adjusting for confounding?				
10.5 Does the plan describe methods for handling missing data?				9.7.2.2
10.6 Is sample size and/or statistical power estimated?				4, 9.5

Comments:

--

Section 11: Data management and quality control	Yes	No	N/A	Section Number
11.1 Does the protocol provide information on data storage? (e.g. software and IT environment, database maintenance and anti-fraud protection, archiving)				9.6
11.2 Are methods of quality assurance described?				9.8
11.3 Is there a system in place for independent review of study results?				13

Comments:

The Final Report will be sent to PRAC for approval.

Section 12: Limitations	Yes	No	N/A	Section Number
12.1 Does the protocol discuss the impact on the study results of:				
12.1.1 Selection bias?				9.9
12.1.2 Information bias?				9.9
12.1.3 Residual/unmeasured confounding? (e.g. anticipated direction and magnitude of such biases, validation sub-study, use of validation and external data, analytical methods)				
12.2 Does the protocol discuss study feasibility? (e.g. study size, anticipated exposure, duration of follow-up in a cohort study, patient recruitment)				9.2.2, 9.9

Comments:

--

Section 13: Ethical issues	Yes	No	N/A	Section Number
13.1 Have requirements of Ethics Committee/ Institutional Review Board been described?				10

ENCePP Checklist for Study Protocols (Revision 3)

Approved

Section 13: Ethical issues	Yes	No	N/A	Section Number
13.2 Has any outcome of an ethical review procedure been addressed?				10
13.3 Have data protection requirements been described?				10

Comments:

As explained in Section 10 of the protocol, this study (healthcare professional survey) does not require ethics approval.

Section 14: Amendments and deviations	Yes	No	N/A	Section Number
14.1 Does the protocol include a section to document amendments and deviations?				5

Comments:

Section 15: Plans for communication of study results	Yes	No	N/A	Section Number
15.1 Are plans described for communicating study results (e.g. to regulatory authorities)?				13
